8.5. Assessment of Safety

Safety of the treatments will be assessed through routine monitoring of AEs.

From screening (for AE onset after the subject signs the ICF), daily during the in-patient phase, then at each visit, and at the Follow-Up and long-term follow-up Visits, the patients will be asked about current AEs or any events observed during the period previous to the visit.

In addition, 12-lead ECG recording, regular measurement of vital signs and

neurological and physical examinations, ophthalmological evaluation, clinical laboratory parameters monitoring, will be made at scheduled follow-up visit. (see Section 8.6.1 for AE recording and reporting) and as described below. At long-term follow-up visits, there will be a short physical examination and clinical laboratory parameters will be monitored.

8.5.1. 12-lead ECG Safety recording

Standard 12-lead ECGs will be recorded as per the Schedule of events in Section 5. Most will be single readings, but where triplicate ECGs are specified, 3 repeat ECGs, with a time difference of about 1 minute between them, will be captured. Instructions for recording and handling of the ECGs will be included in the Study Procedures Manual. Any ECG abnormality confirmed by repeat will be assessed for clinical significance and if so reported as an AE (see AE definition in Section 8.6.1). If out of range at screening, the ECG may be repeated once.

8.5.2. Vital signs

Blood pressure and heart rate will be measured, in the supine position after 10 minutes rest, at times detailed in the Schedule of events (Section 5).

Oral temperature will be measured at screening and on Day -1 (24 h before the morning dose on Day 0).

Blood pressure and heart rate will be measured using using SpaceLabs oscillometric equipment.

Oral temperature will be measured using oral thermometers

During the trial, vital signs will be repeated if they fall outside the following ranges:

- Supine systolic BP: 90–140 mm Hg
- Supine diastolic BP: 40–90 mm Hg
- Supine heart rate: 40–100 beats/min
- Oral temperature: 35.5–37.8°C

If the result of the repeat measurement is still out of range, the Investigator will make an assessment of clinical significance (if the abnormality is assessed as clinically significant, it will be reported as an AE) and decide on an appropriate course of action. If out of range at screening, vital signs may be repeated once.

8.5.3. Neurological and physical examination

Physical examination: will be done by a physician. The following will be examined: general appearance; head, ears, eyes, nose and throat; thyroid; lymph nodes; back and neck; heart; chest; lungs; abdomen; skin; and extremities; and the following systems will be assessed: musculoskeletal and neurological (see below).

Height and body weight will also be measured (at screening) and body weight only on the morning of Day -1. At certain time points, as detailed in the Schedule of events (Section 5), a short physical examination will be performed (to be detailed in the Study Procedures Manual).

Neurological examination will be done by a physician, and will include the following:

alertness, speech, language, and comprehension; cranial nerves; motor exam; coordination/cerebellar function; tremor of the hands, legs and head (postural, kinetic and rest tremor); sensation; gait and postural stability (Pull test); mood; and sleepiness. Full details of the full and short neurological exams will be in the Study Procedures Manual. Abnormalities assessed as clinically significant will be reported as AE (see AE definitions in Section 8.6.1).

8.5.4. Ophthalmological examination (Screening Visit 2 and Day 10)

For Screening Visit 2, subjects will attend a specialist eye hospital for ophthalmology assessments (see Section 8.3.2) to be performed by a Consultant Ophthalmologist (and described in the Study Procedures Manual).

Subjects will be informed that they will need to bring their distance glasses (if applicable) and that, at Screening Visit 2, their near vision will be blurred for approximately 2 h (due to the use of mydriatic eye drops) following the eye-testing procedures. Abnormalities assessed as clinically significant will be reported as AE (see AE definitions in Section 8.6.1).

Subjects will also have an ophthalmological assessment on Day 10.

8.5.5. Clinical Laboratory Safety Assessments

Processing of samples will be done by the HMR Analytical Laboratory in accordance with the laboratory's standard operating procedures, and additional information may be found in the Study Procedures Manual.

The HMR Analytical Laboratory will do safety tests on blood and urine samples using instruments interfaced to a validated laboratory information management system (LIMS). Confirmed abnormal laboratory results (after repeat) will be assessed for clinical significance (CS; see CS assessment below) and reported as AEs if necessary (see AE definition in Section 8.6.1). Data from analysers that are not interfaced will be entered manually into the LIMS.

Collection of samples for laboratory safety tests: Blood will be taken for haematology (2 mL in EDTA), and biochemistry and serology (2 × 2.5 mL in tubes with a gelatin plug). Blood will be taken to measure Hb1Ac (2 mL in EDTA), and for coagulation (3 mL in sodium citrate). Blood samples will be collected into 13 × 75 mm tubes. Urine will be collected in Universal containers. Samples will then be transferred to the laboratory.

Laboratory abnormalities considered AEs:

Laboratory abnormalities assessed as "clinically significant" have to be reported as an AE (refer to AE definition in section 8.6.1) only if they meet at least one of the following conditions:

- The abnormality suggests a disease and/or organ toxicity AND this abnormality was not present at the screening visit, or is assessed as having evolved since the screening visit
- The abnormality results in discontinuation of the study drug
- The abnormality requires medical intervention or concomitant therapy

When reporting an abnormal laboratory result, a clinical diagnosis should be recorded rather than the abnormal value itself, if available (for example, "anaemia" rather than "decreased red blood cell count")

8.6. Adverse Event definitions and reporting

8.6.1. Adverse Event definitions

An *adverse event* will be defined as:

Any untoward medical occurrence in a clinical trial subject administered a medicinal product, and which does not necessarily have a causal relationship with that treatment. An AE can therefore be any unfavourable and unintended sign (eg. an abnormal laboratory finding), symptom, or disease temporally associated with the use of a medicinal product, whether or not considered related to the medicinal product.

Furthermore the definition of an AE includes worsening (in severity and frequency) of pre-existing conditions ("Medical history") before first Investigational Medicinal Product (IMP) administration and abnormalities of procedures (ie., ECG, X-ray, ophthalmologic or neurological examination etc.) or laboratory results which are assessed as "clinically significant". Information on AEs must be evaluated by a physician.

What is not an AE?

- Medical conditions present at the initial study visit that do not worsen in severity or frequency during the study are NOT considered as AEs.

8.6.2. Serious Adverse Event (SAE)

An AE will be defined as serious if it is

- **results in death**
ie Causes or contributes to the death.
- **is life-threatening**
Refers to an AE in which the subject was at risk of death at the time of the AE; it does not refer to an AE that hypothetically might have caused death if more severe.
- **requires in-patient hospitalisation or prolongation of existing hospitalisation**
ie The AE requires at least an overnight admission or prolongs a hospitalisation beyond the expected length of stay. Hospital admissions for surgery planned before study entry, for social reasons, for any elective surgery (ie. plastic surgery) or per protocol or for normal disease management (including treatment adjustment) are NOT to be considered as SAE according to this criterion (ie. if the protocol requires planned hospitalisation).
- **results in persistent or significant disability or incapacity**
ie The AE resulted in a substantial disruption of the subject's ability to conduct normal activities.

- **is an important medical event, i.e. is medically significant.**

Medical and scientific judgment should be exercised in deciding whether other situations should be considered serious events/reactions, such as important medical events that might not be immediately life-threatening or result in death or hospitalisation, but might jeopardise the subject or might require intervention to prevent one of the other outcomes listed above. Any suspected transmission via a medicinal product of an infectious agent is also considered a serious AE/reaction.

8.6.3. Eliciting Adverse Event information

The Investigator is required to report all directly observed AEs and all AEs spontaneously reported by the trial subject using concise medical terminology.

In addition, each trial subject will be questioned about the occurrence of AEs using non-leading questions (eg. "How are you feeling?"), at times specified in the Schedule of events (Section 5).

Each AE will be assessed for severity, and causality (see definitions in Section 8.6.6 and 8.6.7). In addition, each AE is to be classified by the Investigator as serious or non-serious (see definition in Section 8.6.2). This classification will determine the reporting procedure for the event (see Section 8.6.5).

Information on AEs must be evaluated by a physician. Each AE is to be classified by the Investigator as serious or non-serious. This classification will determine the reporting procedure for the event.

Non-serious AEs are to be reported on the CRF, which is to be submitted to DNDi as specified in Section 12.2. In the CRF, a given AE will be recorded only one time per subject, and the severity recorded will be the maximum level reached. If several distinct episodes of the same condition occur, their number will be recorded in the CRF.

SAEs will be reported both on the AE CRF and the SAE forms.

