8.6.4. Adverse Event reporting period

The AE reporting period begins upon subject enrolment in the trial (after signature of the ICF) and ends at the last Long-term Follow-up Visit (Day 120 ±2 days).

All AEs that occur during the AE reporting period specified in the protocol must be reported to DNDi, whether or not the event is considered medication related. In addition, any AE that occurs subsequent to the AE reporting period that the Investigator assesses as possibly related to the investigational medicinal product should also be reported as an AE.

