10.6.5. Adverse events

Throughout the study, all AEs observed by either medical staff or professional collaborators, or reported by the subject spontaneously or in response to a direct non-leading question, will be evaluated by the Investigator and noted in the AE section of the CRF, as described in Section 12.2.

AEs will be coded using the version of the Medical Dictionary for Regulatory Activities (MedDRA) current at the time of database lock.

All AEs will be listed.

An AE will be considered as treatment emergent if it appeared after the first dosing, or if appeared before dosing and worsened after dosing. In case of missing onset date of AE or missing onset time of AE when it appeared the first dosing day, the AE will be considered as treatment emergent (TEAE).

The number of subjects with at least one TEAE will be tabulated by actual treatment and MedDRA system organ class and preferred term.

For each of the following, the number of AEs and the number of subjects with AEs will be summarised by actual treatment as follows:

- TEAEs, by system organ class and preferred term
- drug-related TEAEs, by system organ class and preferred term

Subjects with more than one TEAE will be counted only once, at the maximum causality, for each system organ class and preferred term. AEs with missing severity and/or causality will be treated as severe and possibly related, respectively.

AEs leading to withdrawal, deaths and SAEs will be listed separately (fatal events will be listed separately from non-fatal events).

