14.2 Adverse Events

Adverse events will be coded using the version 21.0 or higher of the Medical Dictionary for Regulatory Activities (MedDRA).

All adverse events will be listed.

The number of subjects with at least one treatment-emergent adverse event (TEAE) will be tabulated by actual treatment and MedDRA system organ class. A treatment-emergent adverse event is defined as an event emerging during treatment having been absent pre-treatment or having worsened relative to pre-treatment¹.

For each of the following, the number of adverse events and the number of subjects with adverse events will be summarised:

- TEAEs by system organ class and preferred term
- TEAEs by system organ class, preferred term and severity
- Drug-related (“related” as recorded by the Investigator) TEAEs by system organ class and preferred term

Subjects with more than one TEAE will be counted only once, at the greatest severity or causality, for each system organ class/preferred term. Multiple TEAEs in a subject will be counted once per system organ class and preferred term. Adverse events with missing severity and/or causality will be treated as severe and related, respectively.

Summaries will be sorted by system organ class and decreasing total incidence of preferred term.

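### Recording each adverse event once per subject loses the timing and severity of repeat episodes over 10 days of dosing; a cheap change would keep them

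*Protocol*

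**What the plan says.** Protocol 8.6.3 sets the CRF rule: "a given AE will be recorded only one time per subject, and the severity recorded will be the maximum level reached". The next sentence adds: "If several distinct episodes of the same condition occur, their number will be recorded in the CRF". Neither document provides for an onset, end, severity or relatedness for each episode.

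AE collection starts at consent (Protocol 8.6.4), so it covers a period before the first dose. Treatment-emergent status is then defined twice:

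- Protocol 10.6.5: "An AE will be considered as treatment emergent if it appeared after the first dosing, or if appeared before dosing and worsened after dosing".
- SAP 14.2: "an event emerging during treatment having been absent pre-treatment or having worsened relative to pre-treatment".

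For the tables, SAP 14.2 says that "the number of adverse events and the number of subjects with adverse events will be summarised", and also that "Multiple TEAEs in a subject will be counted once per system organ class and preferred term". Table template T_AE1 combines the two: subjects counted once per class and term, with the number of AEs in square brackets. The AE listing template (L_AE1_PG) has one onset, one resolution, one duration and one time since last dose per record, plus a Frequency field.

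**The concern.** AEs are the primary safety endpoint (Protocol 2.2.1), and this is the repeat-dose study. Protocol 1.4 reports that treatment-related events in Part 1 of the single-dose study resolved in under 24 h, and that the terminal half-life is 523 h. Short events under daily dosing can return as separate episodes, and a long half-life makes accumulation a real question. A reader will want to know whether a visual or nervous-system symptom comes back after each dose, gets worse, or wears off.

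A rule that keeps one record at maximum severity discards that sequence at collection, where it cannot be restored at analysis. The once-per-term rule in SAP 14.2, by contrast, only condenses records that still exist. Protocol 12.2 makes the CRF the source document for most data, so recovery from elsewhere cannot be assumed.

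**Working it through.** The plan states no figure on this point, so there is none to reproduce. The check follows the recording rule into each planned display.

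**1. Doses, hence possible episodes.** Cohorts 1 and 2 receive one dose on each of Days 0 to 9, which is 10. Cohort 3 receives 10 morning doses plus 9 or 10 evening doses, which is 19 or 20. The range arises because the Protocol Summary, note 8 to the schedule of events and Section 8.3.8 give only a morning dose on Day 9, while Sections 4.3 and 7.1 describe evening doses on Days 0 to 9. Those passages must be reconciled.

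**2. Worst case: one episode after every dose.**

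| | Once daily | Twice daily |
|---|---|---|
| Episodes, one subject | 10 | 19 to 20 |
| CRF records, one subject | 1 | 1 |
| Episodes with no timing held | 9 of 10 | 18 of 19, or 19 of 20 |
| Episodes, six active subjects | 6 × 10 = 60 | 6 × 19 = 114 to 6 × 20 = 120 |
| CRF records, six active subjects | 6 | 6 |

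Counting records gives 6 events; summing the recorded episode number gives 60, or 114 to 120. The count is recoverable. The timing, severity and relatedness by episode are not.

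**3. Treatment-emergent status.** Assume that the single record carries the onset of the first episode (the protocol does not say which), and take one pre-dose and one post-dose episode:

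| Pre-dose | Post-dose | Merged record | Worsened in severity? |
|---|---|---|---|
| none | mild | post-dose onset, mild | not needed; treatment-emergent, correctly |
| mild | mild | pre-dose onset, mild, 2 episodes | no |
| moderate | mild | pre-dose onset, moderate, 2 episodes | no |
| mild | moderate | pre-dose onset, moderate, 2 episodes | yes |

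The last two rows leave the same record, yet only the last worsened in severity. The merged episode number does not help, because it does not separate pre-dose from post-dose episodes.

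**4. How often a pre-dose episode might arise.** If each subject has probability p of a pre-dose episode, the chance that at least one of six active subjects in a cohort has one is 1 − (1 − p)^6. The documents give no p, so a range is assumed:

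- p = 5%: 1 − 0.95^6 = 27%
- p = 10%: 1 − 0.90^6 = 47%
- p = 20%: 1 − 0.80^6 = 74%

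The same AE must also recur after dosing for that subject to be affected, so these are upper limits on the chance of a problem in a cohort.

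**5. Is recurrence plausible at these doses?** Table 1 in Protocol 1.4 gives eye disorders after single doses of the oral solution in 2 of 6 subjects at 10 mg and 1 of 6 at 20 mg. The present trial gives 5 or 10 mg per dose, with a daily maximum of 20 mg.

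**The case against.** The rule is coherent: one row per AE, at its worst, with an episode count. Much of the planned safety output is untouched by merging post-dose episodes. Subjects are counted once per class and term at greatest severity, which maximum-severity recording supports. The severity table (T_AE3) has no event counts. The trial stopping rule in Protocol 7.6.2 counts affected subjects, or a single related serious AE. Serious AEs also have their own form with onset and duration (Protocol 8.6.5). All of this stands.

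Three stronger readings are tempting, and the documents do not support them.

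- A reader might infer that the event counts are wrong. The episode number is collected; the gap is that neither SAP 14.2 nor T_AE1 says whether records or episodes are counted. The CRF is not among the documents, so whether the listing's Frequency field holds that number is unknown.
- A reader might infer that recurring events are generally misclassified as to treatment emergence. That requires a pre-dose episode of the same AE. Even then the definitions play a part: Protocol 8.6.1 treats worsening of a pre-existing condition as a matter of severity and frequency, and under the SAP wording a recurrence at unchanged severity and frequency might not qualify even with its own record.
- A reader might cite the 5 of 6 subjects with eye disorders at 40 mg. That dose is above this trial's 20 mg daily maximum.

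What remains is that no timing, severity or relatedness is held by episode, and that a merged record cannot show whether a pre-dose AE worsened.

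**Conclusion.** The point holds as a cheap improvement. The plan is not wrong as written, but its AE data cannot describe the course of a repeated effect over 10, 19 or 20 doses, which a repeat-dose safety trial would want to report. The recorded onset is incomplete rather than false: it can describe one episode and is silent on the others.

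Treatment-emergent status is uncertain only for subjects with the same AE both before and after the first dose. How many that would be cannot be derived from the documents. Understatement of event counts is conditional on the SAP counting records.

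The figures of 60 against 6, and of 114 to 120 against 6, assume an episode after every dose in every active subject. They mark the outer limit and are not a forecast.

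**What to change.** - **Protocol 8.6.3 and the CRF instructions:** require one record per distinct episode, each with its own onset and end date and time, severity and relatedness. At the very least, keep pre-dose and post-dose episodes of the same AE on separate records.
- **SAP 14.2:** state that the bracketed event counts in T_AE1 count episodes. Also say whether a post-dose recurrence of an AE seen before dosing is treatment-emergent, since separate records supply the data but the definition decides.
- **Unchanged:** subject counts once per class and preferred term, at greatest severity.

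The cost is more AE rows to enter and code, for up to 24 planned subjects who are in-house throughout dosing. At the extreme, that is 10 to 20 rows for one recurring symptom in place of one.

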8.6.4. Adverse Event reporting period

The AE reporting period begins upon subject enrolment in the trial (after signature of the ICF) and ends at the last Long-term Follow-up Visit (Day 120 ±2 days).

All AEs that occur during the AE reporting period specified in the protocol must be reported to DNDi, whether or not the event is considered medication related. In addition, any AE that occurs subsequent to the AE reporting period that the Investigator assesses as possibly related to the investigational medicinal product should also be reported as an AE.

8.6.5. Serious Adverse Event reporting requirements

All serious adverse events (SAE) are to be reported immediately (within 24 hours of awareness of SAE by the Investigator) to the Sponsor Clinical Team (via [contact]), and to DNDi Pharmacovigilance (via [contact]), using the SAE report form. This includes a

description of the event, onset date and type, duration, severity, relationship to study drug, outcome, measures taken and all other relevant clinical and laboratory data. The initial report is to be followed by submission of additional information (follow-up SAE form) as it becomes available. Any follow-up reports should be submitted as soon as possible, and if possible within 5 working days.

SAEs should also be reported on the clinical trial AE case report form (CRF). It should be noted that the form for reporting of SAE (SAE form) is not the same as the AE section of the CRF. Where the same data are collected, the two forms must be completed in a consistent manner, and the same medical terminology should be used.

In addition to immediately reporting SAEs to DNDi, **the Investigator will immediately notify the Research Ethics Committee (REC) of serious adverse events** that occur during this trial, if applicable, in accordance with the standard operating procedures issued by the Research Ethics Service (RES).

A **suspected unexpected serious adverse reaction (SUSAR)** is a suspected adverse reaction related to an investigational medicinal product (as defined in Section 8.6.7) that is both unexpected and serious.

DNDi is responsible for determining the expectedness of the event, using the reference safety information in the Investigator's Brochure. DNDi will notify the Medicines and Healthcare products Regulatory Agency (MHRA) and the European Medicines Agency (EMA) of all SUSARs, and will be responsible for ensuring that the REC is notified of SUSARs, if applicable.

- SUSARs that are fatal or life-threatening must be notified to the MHRA/EMA and REC within 7 calendar days after DNDi becomes aware of the event. Follow-up reports should be provided within another 8 calendar days.
- Other SUSARs must be reported to the REC and MHRA/EMA within 15 days after DNDi becomes aware of the event.

